5.1 Protocol requested treatment

5.1.1 Investigational treatment

The investigational drug, CFZ533 and matching placebo will be prepared by Novartis and supplied to the Investigator site as open-label bulk medication.

Cohorts 1 and 2

The dosage form of the supplied drug is lyophilisate in vial and needs to be reconstituted with water for injection (USP or equivalent), provided by the investigator's site. The placebo control selected for this study is a mixture of inactive excipients, matching the composition of the CFZ533 Corporate Confidential Information for injection.

Table 5-1 Study drug CFZ533 (lyophilisate)

Name	CFZ533
Formulation	Lyophilisate in vial (powder for solution for injection)
Appearance before reconstitution	White lyophilized cake
Appearance after reconstitution	Opalescent to clear, colorless solution
Unit dose	<small>Corporate Confidential Information</small>
Packaging	6 mL Type I glass vials

*The vials contain a 20% overfill to allow a complete withdrawal of the labeled amount of CFZ533

After reconstitution of the lyophilized powder with 1.0 mL water for injection, the resulting solution contains CFZ533 and the excipients L-Histidine, Sucrose and Polysorbate 20, pH 6.0 ± 0.5 .

Cohort 3

The dosage form of the supplied drug is a 'ready to use' aqueous buffered sterile solution also referred to as CFZ533 Concentrate for infusion/solution for injection (liquid in vial). This presentation has the same composition as the reconstituted powder. The same overfill of 20% is included to allow complete removal of the intended dose. There is no placebo for this cohort.

Table 5-2 Study drug CFZ533 (liquid in vial)

Name	CFZ533
Formulation	Solution for infusion/solution for injection
Appearance	Opalescent to clear, colorless solution
Unit dose	Corporate Confidential Information

*The vials contain a 20% overfill to allow a complete withdrawal of the labeled amount of CFZ533

Clinical supplies are to be dispensed only in accordance with the specified study procedures.

An unblinded pharmacist or authorized designee is required to prepare the study drug. Instructions for storage and handling of CFZ533 vials, and preparation of CFZ533 and placebo (in Cohorts 1 and 2) injection are described in the Pharmacy Manual, provided as a separate document.

Of note, CFZ533 vials require storage between 2-8°C.

5.1.2 Additional study treatment

No additional treatment beyond investigational treatment is requested for this trial.

5.2 Treatment arms

The study will have three cohorts.

In the placebo-controlled period of Cohorts 1 and 2, all subjects will be randomized in a 2:1 ratio to one of the following two treatment arms, defined as:

Cohort 1

- CFZ533 active: multiple doses of CFZ533 s.c. injection
- CFZ533 placebo: multiple doses of placebo s.c. injection

In the open-label period, all subjects will receive CFZ533 active treatment of multiple s.c. dosing

Cohort 2

- CFZ533 active: multiple doses of [redacted] CFZ533 i.v. infusion
- CFZ533 placebo: multiple doses of placebo i.v. infusion

In the open-label period, all subjects will receive CFZ533 active treatment of multiple i.v. dosing

Cohort 3

In the open-label Cohort 3, the subjects will be randomized in a 1:1 ratio to one of the following two treatment arms:

- Treatment arm 1: CFZ533 will be given [redacted] weekly on 4 occasions (Days 1, 8, 15 and 22; loading regimen), followed by [redacted] s.c. weekly on 9 occasions (maintenance regimen starting on study Day 29, last dose on Day 85).
- Treatment arm 2: CFZ533 [redacted] i.v. on Day 1, followed by [redacted] c. weekly on 12 occasions (maintenance regimen starting on study Day 8, last dose on Day 85).

The ^{Corporate Confidential Information} [redacted] s.c doses will consist of 4 injections or 2 injections of 1 mL CFZ533 respectively.

5.3 Treatment assignment

Randomization numbers will be assigned in ascending, sequential order to eligible subjects (see [Section 5.5.1](#) for details). The investigator will enter the randomization number on the eCRF.

The randomization numbers will be generated using the following procedure to ensure that treatment assignment is unbiased and concealed from subjects and investigator staff. A randomization list for each cohort will be produced by or under the responsibility of Novartis Drug Supply Management using a validated system that automates the random assignment of treatment arms to randomization numbers in the specified ratio. The randomization scheme for subjects will be reviewed and approved by a member of the Novartis IIS Randomization Group.

Randomization procedure for central management of randomization numbers:

When an eligible patient at a participating study site is ready to be randomized into the study, the steps below will be followed:

- The site designee will complete a Randomization Request form and email to the Novartis designee.
- On receiving the Randomization Request form, the Novartis designee will write the next available randomization number within the randomization list for the corresponding part of the study on the form and email back.
- On receiving the allocated randomization number, the unblinded pharmacist or authorized designee will use the information on the completed form to ensure that the patient receives the correct study medication, according to the provided randomization list.

After inclusion of each new patient, the site designee will countersign the Randomization Request form, and email it back to the Novartis designee to document the correct assignment of the patient's randomization number and the date the patient received their first dose of study medication.

5.4 Treatment blinding

Cohorts 1 and 2 are double-blind: subjects, investigator staff, persons performing the assessments, and data analysts will remain blind to the identity of study treatments according to the specifications provided in [Appendix 6](#). Randomization data are kept strictly confidential until the time of unblinding for the respective person(s). Further information regarding blinding (and unblinding) is presented in [Appendix 6](#).

The identity of the treatments will be concealed by the use of study drugs that are all identical in packaging, labeling, schedule of administration, appearance, taste and odor.

An unblinded pharmacist at the investigator site will prepare the study treatment for injection from the bulk open-labeled supplies.

The blind of the controlled period of the study will be maintained in the open-label period for the investigator and the patient until the end of the study.

The PK/PD bioanalysts will be unblinded during the clinical study, but will not provide individual PK/PD data prior to database lock, to maintain the study blind.

The necessary safety review may lead to the Novartis study team being inadvertently unblinded; however, this information will not be communicated to the investigator.

Unblinding will only occur in the case of patient emergencies (see [Section 5.5.11](#)) and at the time of the interim analysis and at the conclusion of the study.

Cohort 3 will be open-label. However, subjects and investigator staff remain blinded to the study treatment allocation (dosing arm) until first dosing. Further information regarding blinding (and unblinding) is presented in [Appendix 6](#).

5.5 Treating the subject

5.5.1 Subject numbering

Screening number

Each subject screened is assigned a unique screening number. The screening number is a combination of the center number that is provided by Novartis, and a three digit number starting with 001 for each subject which is assigned by the Investigator. Therefore, if the center number is 1 (any leading 0's in the center number are dropped) the screening numbers will be assigned such as 1001, 1002, 1003 in ascending order. If the center number is 2 (or 0002), the screening numbers will be 2001, 2002, 2003 in an ascending order.

Randomization number

If the subject is deemed eligible for the study and will commence dosing, a randomization number will be assigned. Once assigned to a subject, a randomization number will not be reused.

The randomization number becomes the definitive subject number as soon as a subject receives the first dose of the respective study treatment.

There should be a source document maintained at the site which links the screening number to the randomization number (once assigned). This source document should be provided to all appropriate parties (i.e., Central Laboratory) as soon as this is available.

Cohort 1

Subjects will be assigned randomization numbers 5101-5130 in the first stratum (baseline intake of oral corticosteroids = yes) and randomization numbers 5201-5230 in the second stratum (baseline intake of oral corticosteroids = no).

Replacement subjects will be assigned randomization numbers 6101-6130 in the first stratum and 6201-6230 in the second stratum. If a subject requires a replacement, the replacement subject will be assigned a randomization number corresponding to the original subject (e.g., Subject 6103 would replace Subject 5103). Replacements are envisaged only for subjects dropping out for reasons other than safety without at least one post-baseline ESSDAI result.

Cohort 2

Subjects will be assigned randomization numbers 5601-5630 in the first stratum (baseline intake of oral corticosteroids = yes) and randomization numbers 5701-5730 in the second stratum (baseline intake of oral corticosteroids = no).

Replacement subjects will be assigned randomization numbers 6601-6630 in the first stratum and 6701-6730 in the second stratum. If a subject requires a replacement, the replacement subject will be assigned a randomization number corresponding to the original subject (e.g., Subject 6603 would replace Subject 5603). Replacements are envisaged only for subjects dropping out for reasons other than safety without at least one post-baseline ESSDAI result.

Cohort 3

Subjects will be assigned randomization numbers 5801-5840.

5.5.2 Dispensing the study treatment

The investigational drug, CFZ533 lyophilisate in vials and matching placebo (Cohorts 1 and 2), or CFZ533 liquid in vials in Cohort 3 will be prepared by Novartis and supplied to the investigator site as open labeled bulk medication.

For preparation of the study medication, a copy of the randomization schedule will be sent to the unblinded pharmacist at the Investigator's site or to the dispensing contractor.

Appropriate documentation of the subject specific dispensing process must be maintained.

Bulk medication labels will be in the local language, will comply with the legal requirements of each country, and will include storage conditions for the drug but no information about the subject.

5.5.3 Handling of study treatment

5.5.3.1 Handling of investigational treatment

Investigational treatment must be received at the study site by a designated person, handled and stored safely and properly, and kept in a secured location to which only the Investigator and designated staff have access. Upon receipt, the study drugs should be stored according to the instructions specified on the labels. Clinical supplies are to be dispensed only in accordance with the protocol. Technical complaints are to be reported to the respective Novartis CPO Quality Assurance. Storage conditions must be adequately monitored and appropriate temperature/humidity logs maintained as Source data.

The Investigator must maintain an accurate record of the shipment and dispensing of study drug in a drug accountability ledger. Drug accountability will be noted by the Monitor during site visits and/or at the completion of the trial.

All drug supplies are to be used only for this protocol and not for any other purpose. Unless specifically instructed by Novartis, the Investigator must not destroy any drug labels, or any partly used or unused drug supply.

At the conclusion of the study, and, if allowed during the course of the study (e.g., an un-blinded monitor), the Investigator will provide a copy of the drug accountability ledger to the Monitor.

Only after receiving a written authorization by Novartis, the Investigator/designee will send all the unused and partly used drug supplies as well as the empty containers to the address provided at the time of authorization for destruction or have the unused and partly used drug supplies as well as the empty containers destroyed by the site's pharmacist, providing a drug destruction certificate.

5.5.3.2 Handling of other study treatment

Not applicable.

5.5.4 Instructions for prescribing and taking study treatment

CFZ533, or matching placebo (Cohorts 1 and 2 only), will be administered as an s.c. injection in Cohort 1, i.v. infusion in Cohort 2, or i.v. infusion and s.c. injection in Cohort 3 by the study center personnel following the instructions and using the material as described and specified in the Pharmacy Manual.

- In Cohort 1, the subjects will be weighed at the baseline visit and this weight value will be used for study medication preparation and the calculation of the dose.
- In Cohort 2, the dose for administration to subjects will be calculated from the individual subjects' body weight obtained at the most recent pre-dose visit.

- In Cohort 3, the i.v. dose (Day 1) for administration to subjects randomized to treatment arm 2 will be calculated from the individual subject's body weight obtained at Baseline visit. All s.c. doses in this cohort are administered as flat doses (not adjusted to body weight)

A physician shall be available, e.g., by pager, DECT etc. at all other times throughout the study.

All dosages prescribed and dispensed to the subject and all dose changes during the study must be recorded on the Dosage Administration Record eCRF.

5.5.5 Permitted dose adjustments and interruptions of study treatment

Study drug dose adjustments and/or interruptions are not permitted in this study; in case of an AE or for any reason (e.g., non-compliance, operational hurdle) resulting in a deviation from the required dosing scheme, consultation and agreement with Novartis will be necessary to decide whether the subject can continue or needs to be withdrawn from the study. Any change in dosing must be recorded on the Dosage Administration Record eCRF.

In case of notable adverse events, SAEs including loss of efficacy and/or associated PK/PD data collected during the study, changes to a different dosing scheme level may be considered and implemented via a protocol amendment.

Upon review data at interim analysis, dose adjustment for study drug may occur. This will be implemented via a protocol amendment. Details are provided in [Section 9.8](#).

5.5.6 Recommended treatment of adverse events

Parenteral administration of monoclonal antibodies can be associated with acute, severe reactions (occurring within the first few hours post dose) secondary to hypersensitivity, immunogenicity, or ADCC-mediated cell depletion. Although such events are more likely to occur during intravenous administration (infusion reaction), they cannot be fully excluded when the antibody is administered as a subcutaneous injection.

Injection site reactions can also be noted during or after subcutaneous administration and are usually less severe than infusion reactions, however, may still require medical attention and treatment.

In this study, CFZ533 will be administered as intravenous infusion and subcutaneous injection.
Corporate Confidential Information

Patients will be monitored at the site for at least 6 hours post dose or longer in Cohort 1, at least 2 hours post dose or longer in Cohort 2, and at least 1 hour after i.v. infusion and 30 minutes after s.c. injections in Cohort 3 at the discretion of the Investigator to ensure adequate safety monitoring. In case of any signs of an acute reaction, clinical treatment will be provided as determined by the treating physician on a case-by-case basis and depending on the severity, using symptomatic treatment, anti-histamines, NSAIDs, acetaminophen, intravenous fluids, corticosteroids, or adrenaline.

For the management of allergic reaction, anaphylaxis and cytokine release, it is recommended to follow the guidelines by the National Cancer Institute Common Toxicity Criteria (NCI-CTCAE/v4.03, Reference <http://evs.nci.nih.gov/ftp1/CTCAE/About.html>).

When using CFZ533 in a subcutaneous dosing form, plasmapheresis will likely be of limited benefit to decrease the systemic concentration of CFZ533.

Use of rescue medication must be recorded on the Concomitant medications / Significant non-drug therapies eCRF after start of study drug.

5.5.7 Rescue medication

There is no established, approved immunosuppressive treatment for pSS. Patients may receive NSAIDs, paracetamol or symptomatic care at the discretion of the treating physician as outlined in [Section 5.5.8](#). Rescue medicine is to be provided by the study center or personal physician. Use of rescue medication must be recorded on the Concomitant medications/Significant non-drug therapies eCRF after start of study drug.

5.5.8 Concomitant treatment

Use of artificial tears and artificial saliva/salivary stimulants (e.g., cevimeline, pilocarpine) by the patient during participation in the protocol is permitted at the discretion of the treating physician. Amount and frequency of use should be recorded at each visit. For assessments in Cohorts 1 and 2, the salivary stimulants should be stopped within 12 hours prior to, or during assessment of clinical disease outcome measurements. Artificial tears and artificial saliva are to be provided by the study center or personal physician if needed, and should not be used 4 hours prior to, or during assessment of clinical disease outcome measurements.

Currently, concomitant use of corticosteroids is allowed at a dose of max 10 mg per day (prednisone or equivalent) and no immunosuppressives such as cyclosporine, cyclophosphamide, or mycophenolate are allowed. Stable dose of methotrexate (up to 25 mg per week), azathioprine (up to 100 mg per day) and/or antimalarials are permitted. Any other drug with a potential immunosuppressive effect that is not specifically mentioned in the Inclusion/Exclusion criteria, should be discussed with the Sponsor on a case by case basis. If, based on the patient condition (such as severe extraglandular manifestation, or major disease worsening) a corticosteroid dose above 10 mg (prednisone or equivalent) per day or an immunosuppressive medication is necessary, the patient may have to be withdrawn from the study. This will be decided on the basis of a case by case evaluation by both the investigator and Sponsor.

The investigator should instruct the subject to notify the study site about any new medications he/she takes after the start of the study drug.

All prescription medications, over-the-counter drugs and significant non-drug therapies (including physical therapy and blood transfusions) administered or taken within the timeframe defined in the entry criteria prior to the start of the study and during the study, must be recorded on the Concomitant medications/ Significant non-drug therapies section of the eCRF.

Medication entries should be specific to trade name, the single dose and unit, the frequency and route of administration, the start and discontinuation date and the reason for therapy.

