Protocol	A written account of all the procedures to be followed in a trial, which describes all the administrative, documentation, analytical and clinical processes used in the trial.
Part	A single component of a study which contains different objectives or populations within that single study. Common parts within a study are: a single dose part and a multiple dose part, or a part in patients with established disease and in those with newly-diagnosed disease.
Period	A minor subdivision of the study timeline; divides phases into smaller functional segments such as screening, baseline, titration, washout, etc.
Premature subject withdrawal	Point/time when the subject exits from the study prior to the planned completion of all study drug administration and assessments; at this time all study drug administration is discontinued and no further assessments are planned.

Randomization number	A unique identifier assigned to each randomized subject, corresponding to a specific treatment arm assignment.
Stage	A major subdivision of the study timeline; begins and ends with major study milestones such as enrollment, randomization, completion of treatment, etc.
Study completion	Point/time at which the subject came in for a final evaluation visit or when study drug was discontinued whichever is later.
Study drug/treatment	Any drug (or combination of drugs) administered to the subject as part of the required study procedures; includes investigational drug, active drug run-ins or background therapy.
Study drug discontinuation	Point/time when subject permanently stops taking study drug for any reason; may or may not also be the point/time of premature subject withdrawal.
Subject	An individual who has consented to participate in this study. The term Subject may be used to describe either a healthy volunteer or a patient.
Subject Number	A number assigned to each subject who enrolls into the study.
Variable	A measured value or assessed response that is determined in specific assessments and used in data analysis to evaluate the drug being tested in the study.

Corporate Confidential Information

Corporate Confidential Information

Corporate Confidential Information

Corporate Confidential Information

Corporate Confidential Information

Corporate Confidential Information

Corporate Confidential Information

Corporate Confidential Information

Protocol synopsis

Protocol number	CCFZ533X2203

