5.5.9 Prohibited treatment

Use of the treatments displayed in the table below are NOT allowed after the start of study drug until at least four weeks after the last administration of study drug.

Table 5-3 Prohibited treatment

Medication	Action to be taken
Other experimental therapies	Withdrawal may be required on a case-by-case basis
Other biologics	Withdrawal may be required on a case-by-case basis
Immune suppressive agents	Withdrawal may be required on a case-by-case basis
Any medication that, as judged by the Investigator, is the primary cause of dry mouth in the patients	Withdrawal may be required on a case-by-case basis
Live vaccination	Withdrawal immediately

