Subjects who discontinue study treatment should NOT be considered withdrawn from the study UNLESS they withdraw their consent (see [Section 5.5.11](#)). They should return for the assessments indicated by an asterisk (*) in the assessment table. If they fail to return for these assessments for unknown reasons, every effort should be made to contact them as specified in [Section 5.5.12](#).

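### Protocol 5.5.5 and 5.5.8 let a consenting patient be withdrawn from the study case by case, an exit that 5.5.10 reserves for withdrawn consent, so loss of Week 13 ESSDAI can depend on outcome

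*Protocol*

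**What the plan says.** Several parts of the protocol deal with patients who go off plan without withdrawing consent.

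- **5.5.8 Concomitant treatment.** If the patient's condition, including major worsening, requires corticosteroid above the cap or an immunosuppressive, "the patient may have to be withdrawn from the study". On who decides: "This will be decided on the basis of a case by case evaluation by both the investigator and Sponsor".
- **5.5.5 Dose adjustments and interruptions.** After any departure from the dosing scheme, whether from an adverse event, non-compliance or an operational problem, agreement with the sponsor is needed "to decide whether the subject can continue or needs to be withdrawn from the study".
- **5.5.9, Table 5-3.** For four of the five prohibited classes: "Withdrawal may be required on a case-by-case basis". For live vaccination, withdrawal is immediate. The table does not say whether this means from treatment or from the study.
- **5.5.10 Discontinuation of study treatment.** Major worsening is listed among the reasons treatment must stop. The section then says: "Subjects who discontinue study treatment should NOT be considered withdrawn from the study UNLESS they withdraw their consent". These patients return for the assessments marked with an asterisk.
- **Glossary.** Stopping study drug and premature subject withdrawal are separate entries. For the latter, "at this time all study drug administration is discontinued and no further assessments are planned".
- **Assessment schedule.** In Cohort 1 the asterisk marks V777, the end-of-study visit, where ESSDAI is ticked. Its footnote asks patients who discontinue the study to complete that set. The Cohort 2 footnote with the same content carries the number 3, not an asterisk.
- **Missing data.** Protocol 9.4.3 names 5.5.10 as the basis for treating missing values as approximately missing at random. The SAP's subsection on missing values refers to the protocol's discontinuation guidelines in general and promises a check of the assumption without naming a method.

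**The concern.** A patient whose disease worsens and who needs rescue falls under both 5.5.8 and 5.5.10. One section allows the patient to leave the study; the other stops treatment and keeps the patient in. Nothing says which section takes precedence, and 5.5.8 gives no criterion for the choice.

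This matters for the primary efficacy analysis because the trigger in 5.5.8 is close to the endpoint itself. Missing at random requires that, given the recorded ESSDAI values, exit does not depend on the unrecorded ones. On the Cohort 1 schedule, ESSDAI is scored on Days 15, 29, 57 and 85, which leaves two 28-day gaps. A flare inside a gap can lead to an exit before any score reflects it. Section 9.4.3 does not mention the exit routes in 5.5.5 and 5.5.8, so the safeguard it cites does not cover them.

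**Working it through.** **Step 1. The sections side by side.**

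| Situation, consent not withdrawn | Section | Status in the study |
|---|---|---|
| Major worsening | 5.5.10 | Treatment stops; patient stays in |
| Rescue above the cap or immunosuppressive, e.g. major worsening | 5.5.8 | May be withdrawn from the study |
| Dosing deviation | 5.5.5 | Continues, or is withdrawn from the study |
| Prohibited treatment | Table 5-3 | Withdrawal, object not stated |
| After leaving the study | Glossary | No further assessments |
| After leaving the study | Schedule footnotes | Completes a set of assessments |

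Rows 1 and 2 conflict for the same kind of patient. Row 3 conflicts with 5.5.10 because it allows an exit without withdrawn consent, but its triggers are not mainly disease worsening. Row 4 is ambiguous. Rows 5 and 6 conflict with each other.

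**Step 2. The plan's own figures.** Inputs from Protocol 9.6 and 9.4.2: SD 5, 16 active and 8 placebo, one-sided 10% test, and an estimated difference of at least 5 points.

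SE = 5 × √(1/16 + 1/8) = 2.165.

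The 5-point criterion is the binding one, so the chance of success at true difference d is about 1 − Φ((5 − d)/2.165). Simulating both criteria together (t-test, 22 df) gives:

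| True difference | Protocol | Recomputed |
|---|---|---|
| 0 | about 1% | 1.0% |
| 2 | below 10% for differences under 2 | 8.2% |
| 5 | about 51% | 49.9% |
| 7 | about 83% | 82.2% |

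The protocol's figures reproduce to within 2 points.

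**Step 3. Loss unrelated to outcome.** With 14 v 7 patients the chance at a true 7 is 80.6%, and with 12 v 6 it is 78.8%. Smaller numbers alone cost little; the issue is bias.

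**Step 4. Loss related to outcome (assumed values).** The documents give no exit rate by reason. Assume that lost patients end 3 to 7 points worse than the model predicts from their recorded values, that no later value is obtained, and that the SE stays at 2.165. Then

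shift in estimated benefit = points worse × (share lost on active − share lost on placebo).

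| Lost, active v placebo | Shift | Chance at true 7 | Chance at true 0 |
|---|---|---|---|
| 10% v 20% | 3 × (−0.1) = −0.3 to 7 × (−0.1) = −0.7 | 78% to 73% | 0.7% to 0.4% |
| 20% v 10% | +0.3 to +0.7 | 86% to 89% | 1.5% to 2.3% |
| 10% v 10% or 20% v 20% | 0 | 82% | 1.0% |

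Cohort 2 plans about 30 patients at 2:1, so about 20 and 10. The first row is then 2 + 2 = 4 exits and the second 4 + 1 = 5. Both fall within the 30 − 24 = 6 non-completers the plan expects from all causes.

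**The case against.** The best case for the plan is that this is a wording slip with little effect on the data. Several parts of that case stand.

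- **Exit is mostly discretionary.** A reader might infer that these sections remove every such patient. They do not: apart from live vaccination, the wording is permissive. Table 5-3 can also be read as withdrawal from treatment, since 5.5.10 itself puts rules for stopping treatment under a heading about subject withdrawal.
- **Data loss is not total.** A reader might infer from the glossary that nothing is recorded after exit. The schedule footnotes ask study discontinuers for a set of assessments, which in Cohort 1 includes ESSDAI. Earlier ESSDAI values also stay in the longitudinal model.
- **Safety follow-up does not simply end.** Section 7.1 follows adverse events to resolution or until judged permanent, 7.2 takes serious events to 30 days after the last study visit, and Section 6 requires a 30-day safety contact.
- **Unblinded decisions are not shown.** Section 5.4 concedes that "The necessary safety review may lead to the Novartis study team being inadvertently unblinded", but adds that the investigator will not be told. Table 18-1 keeps the clinical trial leader and translational medicine expert blinded during treatment.
- **5.5.10 is itself limited.** It secures only the asterisked assessments, so a Week 13 ESSDAI can be missed under that section too. Letting 5.5.10 alone govern would not close the gap.

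The conflict remains. Permissive wording with no criterion leaves exit after worsening to judgement. The V777 set does not by itself provide a Week 13 value: the visible text does not say whether it is done at exit or on its scheduled day, or how an off-schedule score would enter the SAP's model by visit.

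**Conclusion.** The concern holds in a limited form. Sections 5.5.5 and 5.5.8 allow study exit for consenting patients, against 5.5.10, and in 5.5.8 the trigger can be the worsening that the primary endpoint measures. Section 9.4.3 therefore relies on a rule that other sections can override. Table 5-3, the glossary and the schedule footnotes add ambiguity about what is collected afterwards.

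Neither the size nor the direction of any bias can be derived from the documents. The 0.3 to 0.7 point shift, and the matching fall from 82% to between 78% and 73% or rise to between 86% and 89%, rest on the assumed loss shares and the assumed 3 to 7 points.

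A reader might infer a one-directional bias against the drug. For example, if 1 to 3 of about 10 placebo patients were lost, each 5 to 7 points worse, and nobody on active were lost, the shift would be 1 × 5/10 = 0.5 to 3 × 7/10 = 2.1 points. That needs every such exit to be on placebo, which nothing in the documents supports; Protocol 3.6.1 itself says no statement on efficacy can yet be made. The sample-size arithmetic is unaffected.

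**What to change.** Reconcile 5.5.5, 5.5.8, Table 5-3, 5.5.10, the glossary entry on premature withdrawal and the schedule footnotes for all cohorts, so that:

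1. leaving the study is kept separate from stopping study treatment, and each use of withdrawal says which is meant;
2. unless consent is withdrawn, the scheduled ESSDAI assessments to Week 13 and the safety assessments are still collected, stated outright and not left to an asterisk that differs between cohort tables;
3. rescue use is flagged in the data, and the reason for any exit before Week 13 is recorded before unblinding.

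Whether treatment stops in each situation stays with the sponsor and investigator; this point proposes no clinical rule.

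The cost is wording in a handful of places, a few extra visits by patients already enrolled, and scores obtained after rescue that the analysis must identify by the flag.
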